Breathing Counts
NCT03065205
Protocol version date 12.18.17

COMIRB Protocol

COLORADO MULTIPLE INSTITUTIONAL REVIEW BOARD
[name] [contact] [contact]

Protocol #: 16-1845

Project Title: Breathing Counts

Principal Investigator: [name]

Version Date: 12-18-17

I. Hypotheses and Specific Aims:

Adherence to asthma medications has been associated with good asthma control in children¹, however adherence to asthma medications is poor.² Children who are hospitalized due to their asthma are at a significantly high risk of re-hospitalization³, and represent a particularly high risk group. Successful control of asthma in a high-risk population requires a network of care providers who communicate relevant up-to-date information and support asthma control. Additionally, lay health worker interventions have been shown in some cases to decrease missed school days and parental work days.⁴ We propose to evaluate the efficacy of an asthma navigator program in a high-risk population of patients at Children's Hospital Colorado. We will evaluate the ability of the program to improve health outcomes of children who have asthma and who are at high-risk of re-hospitalization. The project will also evaluate the ability of the navigator program to increase the number of stakeholder communications amongst school nurses, program navigators, physicians, caregivers and children.

Specific Aim 1: Evaluate whether or not the addition of an asthma navigator to the current clinical standard of care will lead to sustainably increased levels of adherence compared to historical rates.

Hypothesis: By providing up to date adherence rates to the patient's medical care team and by addressing patient identified barriers, we hypothesize that the addition of an asthma navigator to the standard of care at Children's Hospital will increase asthma medication adherence rates, and that these adherence rates will be sustained over the 3-6 month monitoring period.

Specific Aim 2 Evaluate whether or not the addition of an asthma navigator results in increased levels of communication between PCPs, specialty providers and school nurses.

Hypothesis: The addition of an asthma navigator will result in increased emails and general communication between various providers in a patient's care team.

Specific Aim 3 Evaluate whether or not other asthma related outcomes (measures of asthma control, asthma related quality of life, presence of a school asthma action plan, among others) are altered with the addition of an asthma navigator to a patient's care team.

Hypothesis: The addition of an asthma navigator will improve other markers of asthma control and quality of life. We anticipate an increase in asthma control and increase in the number of patients with a school asthma action plan.

II. Background and Significance:

Adherence to asthma medications is poor

Adherence to asthma medications is poor, especially in high-risk populations,⁵ and even with monitoring studies show adherence worsens over time.⁶ The large Childhood Asthma Management Program study found that 75% of children studied had adherence levels of less than 80% when measured objectively.⁷ In fact, one review of previous attempts to measure adherence to asthma medications utilizing electronic monitoring devices showed adherence rates between 28-73%, with only one study showing an adherence rate above 90%.⁸

Asthma morbidity is a significant public health problem.

Over eight percent of children in the US carried a diagnosis of asthma in 2013, and 58% of those children had an asthma exacerbation in that year.⁹ Asthma exacerbations/hospitalizations remain a significant source of healthcare expenditures¹⁰

Inhaled corticosteroids have been shown to significantly improve asthma control

The use of low-dose ICS in asthmatic children and adults has been shown to significantly decrease the rate of asthma-related hospitalization¹¹ and asthma related death.¹² Additionally, chronic use of inhaled corticosteroids has been shown to improve asthma control.¹³

Adherence has been correlated with some improved asthma outcomes.

Previous evaluations of adherence using electronic monitoring devices have shown lower adherence rates to be correlated with higher levels of healthcare utilization,¹⁴ and worsened levels of asthma control^{15,16} A small study of Australian children showed a trend toward improvements in lung function with greater adherence, however this failed to reach statistical significance.¹⁷ The correlation of adherence to other asthma outcomes including exacerbations and various markers of lung function/inflammation in high risk children has not yet been studied.

Non-adherence disproportionately affects a high-risk population of children with asthma.

High-risk children are disproportionately of color, have low household levels of education and income, attend poorer performing schools, come from lower socio-economic background.¹⁸ Poorly controlled asthma contributes to poor school performance by disrupting sleep and causing missed days of school^{19,20}, and associations between poor asthma control and missed school are higher among minority children.²¹ Researchers have suggested possible determinants of non-adherence including concerns about medication adverse effects, belief that asthma is not a serious problem, belief that medications are not helping, and preference for a non-pharmacological approach, among others.²² In order to address both the persistent high levels of morbidity associated with asthma and increasing disparities, new approaches to asthma management are needed to more effectively deliver evidence-based preventive treatments and identify children who need a more intensive, stepped up treatment plan. While some interventions based in schools, in the home, or in the community have shown promise,²³⁻²⁵ important limitations have included lack of coordination with community health care providers (HCPs), lack of involvement of schools and the community, inability to monitor medication adherence and lack of sustainability. In short, we aim to reduce health disparities with this program by targeting the highest risk asthma patients, those admitted to the hospital inpatient or emergency department with an asthma exacerbation, which tend to be disproportionately minority patients, and utilize new and innovative technology to improve care for these patients.

III. Preliminary Studies/Progress Report:

We have been conducting a pilot study evaluating the use of electronic adherence monitoring devices in the pediatric asthma population. We have collected preliminary data on the usability of these devices in our population of children aged 6-17. Preliminary evaluation of this data has shown that the devices are largely well tolerated, and data from the devices is accessed often by providers. Most patients feel comfortable utilizing smartphone applications, and the majority of patients found the devices easy to use.

IV. Research Methods

A. Outcome Measure(s):

A table of outcomes to be collected during the study time period is give below (table 1). A detailed description of the outcome follows.

	Outcome Measure	Visit 1 (admission visit)	Visit 2 (2 months)	Visit 3 (4 months or end of study)	Visit 4 (6 months or end of
--	-----------------	---------------------------------	-----------------------	--	-----------------------------------

					study)
Aim 1	Adherence (continually monitored during trial)		X	X	X
Aim 2	Communication among providers	X			X
Aim 3	Asthma Related Health outcomes	X	X	X	X

- a. Adherence- measured on adherence monitoring devices. The rate of daily prescribed controller medication use will be monitored. For example, if an individual is prescribed two doses per day and the monitoring device records one doses, then the daily adherence measure will be 1/2 or 50%. The outcome measure will be continuously gathered via the Propeller Health monitoring device ® (Madison, WI). Rate of monthly adherence will be calculated between study visits,
- b. Communication between providers. Communication between providers will be measured in a number of ways. Providers include nurses, parents, physicians and patients. In order to measure any change in communication the following communication metrics will be monitored.
 - i. Number of emails sent between providers will be assessed if email is used as the primary means of communication.
 - ii. A subset of provider teams will possibly be enrolled in asynchronous communication monitoring. This is a method of HIPAA compliant messaging, which involves providers utilizing an application or website, and communicating securely within that platform. We plan to utilize the Stich platform, which is marketed as HIPAA compliant (<https://www.teamstitch.com>). We are currently on a waiting list to possibly test the technology.
 - iii. Providers will be surveyed before and after the intervention to determine if they felt that the navigators adequately improved communication regarding specific patient related issues.
- c. Other asthma related outcomes including asthma control test, symptom assessments, asthma related readmissions or revisits, missed school days, and provider satisfaction.
 - i. Asthma Control Test, a self (or in the case of this study, phone administered)-administered questionnaire with 5 questions which summarizes asthma control, will be used to record asthma control in children 12 or older.
 - ii. Childhood Asthma Control Test (or in the case of this study, phone administered), a parent and child administered questionnaire, will be used to record asthma control for children 6-11 years of age.
 - iii. Pediatric Inhaler Adherence Questionnaire, a self (or in the case of this study, phone administered) survey of barriers to medication adherence
 - iv. Parent attitudes towards medications and barriers to adherence.
 - v. Changes in adherence barriers and behaviors to improve adherence over time
 - vi. The number of asthma related readmissions or revisits between study visits will be self-reported.

- vii. The number of missed school days between visits will be self-reported.
- viii. Provider satisfaction will be recorded using the pre-post surveys

B. Description of Population to be Enrolled:

- a. Children admitted to Children’s Hospital Colorado inpatient or emergency department with a primary diagnosis of asthma exacerbation.
 - i. Inclusion criteria-patients
 - 1. Age 6-17 years
 - 2. On a controller medication at baseline
 - ii. Inclusion criteria-providers
 - 1. Aged 18-70
 - 2. Caring for a patient that is enrolled in the study
 - iii. Exclusion criteria
 - 1. Primary language other than English or Spanish (smartphone application only available in these languages)
 - 2. Homeschooled or not in school
 - 3. Significant developmental delay, cystic fibrosis, interstitial lung disease, tracheostomy/ventilator dependence
 - 4. Following up with a pulmonary or allergy provider outside of the CHCO system

C. Study Design and Research Methods

The proposed study is a single center trial at Children’s Hospital of Colorado, designed to evaluate the effects of a navigator program on medication adherence, provider communication and other asthma related health outcomes. Participants will be recruited from the population of patients between the age of 6 and 17 years admitted to Children’s Hospital Colorado inpatient or emergency department with a primary diagnosis of asthma exacerbation. Investigators plan on a one-year enrollment period and will follow each study participant for 3-6 months.

Recruitment

Upon admission hospital staff will identify potential participants based on the admission medical record. Patients will be approached by research staff and asked if they would like to participate in the study. A member of the research team (principally, the research coordinator) will do the recruiting. The research coordinator will explain the study and enroll subjects. Estimated duration is 45-60 minutes depending upon the patient.

Consent/Assent

We will obtain a signed parental permission form and an age-appropriate assent form for participants younger than 18 years. Consent will be obtained by a member of the research team (principally, the research coordinator or a research assistant). It will be made clear to patients that the research team is not part of the treatment team.

Study Design

We plan to enroll a total of 100 patients. and up to 400 providers. Patients enrolled will be provided and trained on using the adherence monitoring prior to discharge (sensors will be placed on discharge controller and quick-relief medication). Participants will also be enrolled in the smartphone application that will give them feedback about their medication usage. Once enrolled in the application, patients will receive push notification reminders to use their medications, as well as be able to access their adherence information in real time. Caretakers will also be given the

option to have access to their child's adherence information. The smartphone application also has portions dedicated to education about asthma triggers. Patients will be set up with a pulmonary or allergy follow up within 2-4 weeks of discharge. Patient's pulmonary or allergy providers will also be enrolled in the propeller health system, with access to the propeller health dashboard. Once providers receive access, they will be able to log-in and view all of their patients in list format. They will be able to see up to the minute data on patient adherence at any time that they choose to log-in to the dashboard. Providers will also receive email notifications if their patient has not used their controller medications for 7 days, or if their patient has had a significant increase in quick-relief medication use, indicating a worsening of asthma status (see figure 1 below). Patients will be monitored for a total of 3-6 months. The asthma navigator will contact the families at 2, 4 and 6 months post-enrollment, and discuss the patient's recorded adherence with the families. If a patient is enrolled for 4-5 months, we will discuss adherence at 2 and 4/5 months. If a patient is only enrolled for 3 months, we will discuss adherence at 2 and 3 months. Additionally, they will discuss any barriers to adherence that the family may be experiencing, and make referrals to social work as necessary, as well as attempt to brainstorm ways to improve adherence with the families. Additionally, the asthma navigator will collect each patients' adherence data and create an adherence report, which will be distributed on a monthly basis to the patient's primary care provider, pulmonary/allergy provider, and school nurse via email. The asthma navigator will be monitoring communications between the providers and marking the numbers of communications.

At the time of enrollment, patients will be asked for permission to contact the child's primary care provider and school nurse. If these providers agree to participate in the study, surveys will be sent to all providers of patients (PCPs, school nurses and specialists) to determine if they found the navigator to be helpful, and to see if communication increased due to the intervention. Additionally, the research coordinator will be monitoring the provider portal to ensure that patients' devices are regularly syncing with their phone's Bluetooth, and contact any patients whose devices are not syncing normally. At the study's conclusion, we will plan to have the families return the devices to the research coordinator via US mail. After the conclusion of the study, families will be contacted by the research coordinator to ask if they would be willing to evaluate the navigator via the PSN-I navigator assessment tool. The navigator assessment tool will be used to evaluate utility of the navigator themselves. This is a tool that has been utilized previously in this context to evaluate efficacy of navigator programs. This will only be evaluated at the end of the study. There will be no reimbursement for time for this last survey.

If a patient is having difficulties with syncing their sensors to their phone, we will provide them with a hub to collect the sensor data.

D. Description, Risks and Justification of Procedures and Data Collection Tools:

There will be no medical procedures done during this study. The data collection will occur via surveys, and data collected from the adherence devices. Risks of data collection include accidental disclosure of information, though steps will be taken to prevent this. Also, there is a GPS capability of the devices, so there is a risk of disclosure of patient's location patterns.

E. Potential Scientific Problems:

We are aware that we are underpowered to fully evaluate some of the outcomes that we are interested in obtaining. Additionally, we are limited to single group analysis by request of the funding agency (rather than also having a control group), so we are limited in our ability to make full comparisons. However we would like to undertake this study as a pilot evaluation for the use of the asthma navigator in this population, utilizing adherence monitoring technology to better understand the influence of these evaluations.

F. Data Analysis Plan:

Analysis plan

Demographic information including age, sex, race, and other baseline clinical information upon recruitment including duration of asthma, C-ACT score, ACT score, asthma symptoms, lung function, prescribed medication, and asthma related health care use in the previous year will be obtained at enrollment. The distributions of outcomes will be examined for normality using the Anderson-Darling Test. Dependent upon the distribution we will use the Wilcoxon rank-sum test, Mann-Whitney U test or paired T-test to test for significant changes in outcomes during the study period. Longitudinal patterns of adherence will be examined graphically.

Monthly rates of adherence, asthma symptoms, asthma control scores and monthly missed number of school days and number of hospitalizations will be calculated by study arm. Survey information from patients, caregivers, physicians and navigators on the navigator intervention will be reviewed by study staff and summarized qualitatively. Number of rehospitalizations will be obtained via chart review at 1 month, 6 months and 12 months post hospitalization.

The cost-effectiveness of the navigator intervention will be summarized based on medical resource utilization (direct) and loss of productivity (indirect). Medical resources utilization will include medical care resource utilization, asthma medication variables, navigator time and salary, while loss of productivity will be measured using the number of hours caretaker missed work due to participant's asthma, number of hours dependent participant missed school due to his/her asthma, and number of hours independent participant missed work due to his/her asthma. Unit costs will be applied to healthcare resources and loss of productivity and summed to obtain total costs for each subject. Average costs for the study group will be presented.

Power and Sample Size

The study is limited by time frame and funding for a one year recruitment period. The primary goal of the study is to provide preliminary information on the effect of a navigator program on the patient and caregiver response to asthma disease control. As a pilot and feasibility study, investigators have chosen to enroll a total of 100 patients and up to 400 providers. Through past clinical experience, we know that some months of the year are higher risk for asthma exacerbations, so we expect to screen more patients during the fall and winter than summer or spring. Considering the variable clinical case load Investigators plan on enrolling an average of 10 participants per month. Anticipating an enrollment rate of approximately 20% (in 2015, there were >600 asthma related admissions at Children's Hospital Colorado), investigators state they should be able to enroll up to 100 patients within one year. We plan to enroll up to 4 providers per patient with a simple pre-post survey as well.

The primary hypothesis of interest is to test whether change in adherence rates are different from zero. The smallest detectable difference was based on a paired sample t-test between pre and post adherence scores with a Type I error rate of 0.05 and 90% power. Based on previous studies⁸, investigators assumed a mean adherence rate of 50% with a standard deviation of 22%.

Table X:	
N	Δ
100	8%
65	10%
30	15%

Table X lists the smallest detectable difference (Δ) for by sample size. For the primary aim investigators will be able to detect a change of 8% or more in percent adherence during the study period with the available 100 patients.

F. Summarize Knowledge to be Gained:

- a. **Utility of an asthma navigator in addition to electronic adherence monitoring in improving adherence to asthma medications**
- b. **Utility of an asthma navigator in improving communication amongst all of a patient's medical providers**
- c. **Utility of an asthma navigator in improving other asthma control related outcomes.**

Asthma Control Classification

Control is computed based on taking the entry with the worst outcome in the following age-based tables:

Asthma Control Classification (Age 5-10)

(Age 5-11)	Asthma	Control	Classification
	Well controlled	Not well controlled	Very poorly controlled
Symptoms (manually entered)	≤ 2 days/week but not more than once on each day	> 2 days/week or multiple times on ≤ 2 days/week	Every day in previous week

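### For asthma control scores and symptoms, change measured from the admission visit mixes recovery from the qualifying exacerbation with any navigator effect, and the plan names no other Aim 3 contrast

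*Combined protocol and SAP*

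**What the plan says.** Section IV.B enrols children admitted to the "inpatient or emergency department with a primary diagnosis of asthma exacerbation". In the outcome table of section IV.A the first column is "Visit 1 (admission visit", followed by visits at 2, 4 and 6 months (or end of study), and the Aim 3 row is marked at all four: "Asthma Related Health outcomes X X X X". The same section defines the Aim 3 set as "Other asthma related outcomes including asthma control test, symptom assessments, asthma related readmissions or revisits, missed school days, and provider satisfaction". Asthma control is scored on the ACT from age 12 and on the C-ACT at ages 6 to 11.

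Section IV.F places the baseline ACT, C-ACT and symptom values in the same list as "lung function, prescribed medication, and asthma related health care use in the previous year will be obtained at enrollment". It then names two rank tests and a paired t-test "to test for significant changes in outcomes during the study period". It does not say which visits are compared for Aim 3.

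The Aim 3 hypothesis in section I credits the navigator with improvement: "We anticipate an increase in asthma control". On timing, section IV.C says "The asthma navigator will contact the families at 2, 4 and 6 months post-enrollment". It also has the navigator email monthly adherence reports to the child's providers and school nurse, and arranges a specialist visit 2 to 4 weeks after discharge. Section IV.E acknowledges that the funder asked for a single group, that comparisons are therefore limited, and that the study is a pilot.

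**The concern.** The baseline for these outcomes coincides with the event that made the child eligible. Children chosen at a bad moment tend to be better later, both because the attack resolves and because an extreme value is usually followed by a less extreme one. A one-group test against zero change cannot tell that improvement from a navigator effect, and both point the same way as the hypothesis. The plan has no pre-exacerbation value, no stabilised post-discharge baseline and no outside comparator for asthma control; the historical comparison in Aim 1 concerns adherence only. At stake is whether a significant rise in ACT or C-ACT, or fall in symptoms, could be offered as support for Aim 3.

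**Working it through.** **Plan's own figure.** There is none for Aim 3. The only power figures, in Power and Sample Size, concern adherence: 8, 10 and 15 points detectable with 100, 65 and 30 children (paired t-test, alpha 0.05, 90% power, SD 22). With 22 as the SD of the change and a two-sided test, I get 7.2, 9.0 and 13.5. The printed values return if 22 is the SD of a single score and the pre-post correlation is about 0.38, which the plan does not state. That mismatch does not bear on this point; only the 100 patients and the 0.05 level carry over.

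**Inputs.**
- n = 100 patients (section IV.C, Study Design), assuming no loss.
- Two-sided alpha 0.05. The level is the plan's, stated for adherence; applying it to Aim 3 and taking it as two-sided are assumptions.
- True navigator effect = 0.
- d = mean recovery divided by the SD of the within-child change. This is assumed, because the documents give neither a recovery size nor an SD for these outcomes.
- n = 50 per instrument, as an illustration. ACT and C-ACT divide the sample at age 12, and the age split is not given.

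**Formula.** The paired t statistic follows a noncentral t distribution with n − 1 degrees of freedom and noncentrality d√n. The chance of a significant result is P(|T| > t), where t is the 0.975 quantile: 1.984 for n = 100 and 2.010 for n = 50.

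| d (assumed) | d√100 | Significant, n = 100 | d√50 | Significant, n = 50 |
|---|---|---|---|---|
| 0 | 0 | 5% | 0 | 5% |
| 0.1 | 1.0 | 17% | 0.71 | 11% |
| 0.2 | 2.0 | 51% | 1.41 | 28% |
| 0.33 | 3.3 | 90% | 2.33 | 63% |
| 0.5 | 5.0 | 99.9% | 3.54 | 93% |

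For d above zero, nearly all of these results point towards improvement.

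**From regression to the mean to d.** Suppose the group mean at admission is k SDs worse than usual, and scores on two occasions correlate r. The expected change is k(1 − r) and its SD is √(2(1 − r)), so d = k√((1 − r)/2). For k = 0.5 and r = 0.5, d = 0.5 × 0.5 = 0.25. With n = 100 and r from 0.7 down to 0.3:
- k = 0.25: d = 0.10 to 0.15, significant 16% to 31% of the time;
- k = 0.5: d = 0.19 to 0.30, significant 48% to 83%;
- k = 1: d = 0.39 to 0.59, significant 97% to more than 99.9%.

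**What Visit 2 offers.** The first scheduled family discussion is at 2 months, so Visit 2 is past the acute phase and precedes most direct navigator contact. The interval from Visit 2 to the end of study is 6 − 2 = 4 months for a child followed for 6 months, 4 − 2 = 2 months for one followed for 4, and 3 − 2 = 1 month for one followed for 3.

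**The case against.** The plan never states that Visit 1 is the Aim 3 reference. That is right: the contrast is inferred from the outcome table and section IV.F, as the only one that starts before the intervention. Leaving it open is itself a gap, and it does not rule out the biased choice.

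Section IV.E already discloses the missing control group, and Power and Sample Size makes adherence the primary hypothesis and describes the aim as preliminary. This lowers the stakes. But the caveat is general: it does not mention recovery from the index attack, and it changes neither the test nor the hypothesis the test would be read against.

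A reader might infer that the Aim 3 test is almost certain to be significant whatever the navigator does. The documents do not support that. It holds only if recovery is large relative to the spread of the changes; at 0.1 SD the rate is 17% with 100 pairs and 11% with 50. Nor do they give the recall window of the scores, which affects how far an admission score reflects the attack.

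A reader might also infer that Visit 2 is a clean pre-navigator baseline that should replace Visit 1 as the only tested reference. That also goes too far. Giving the care team current adherence rates is part of the intended mechanism (section I, Aim 1), and the monthly reports can start before month 2. The plan does not say that Visit 2 scores are taken before that visit's discussion. Season, specialist care and app reminders still act after Visit 2.

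**Conclusion.** The point holds for the ACT, the C-ACT and symptoms. A significant change from the admission visit cannot count as evidence for the Aim 3 hypothesis, because recovery alone moves the result the same way and the design has nothing to separate the two. The direction of the bias follows from the enrolment rule and the visit schedule. Its size does not: the false-positive rates run from about 17% to 99.9% with 100 pairs, and from 11% to 93% with an assumed 50 per instrument, for assumed recovery between 0.1 and 0.5 SD of the change. All exceed the nominal 5%.

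A reader might extend this to every Aim 3 outcome. It does not apply in the same way to school action plans or provider satisfaction. Readmissions and missed school days are counted between visits and have no clearly defined baseline value.

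**What to change.** In section IV.F, for the ACT, the C-ACT and symptoms:

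1. Report the change from Visit 1 as an estimate with a confidence interval, labelled as including post-exacerbation recovery. State that a significant change from Visit 1 will not be used to support the Aim 3 hypothesis.
2. Beside it, report the within-patient change from Visit 2 to the end of study, with the interval length given, as the contrast less affected by acute recovery.
3. State the limits of that second contrast. It is still uncontrolled (season, specialist care, app reminders), it omits any effect of reports sent before month 2, and it covers only about one month for children followed for 3 months.

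This changes analysis wording only, since Aim 3 outcomes are already scheduled at every visit. The cost is that Aim 3 will support a weaker statement about asthma control.

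### The communication outcome counts parents and patients as providers, so the Aim 2 message count could mix family contact with contact among medical providers

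*Combined protocol and SAP*

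**What the plan says.** All references are to the combined protocol and SAP.

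- **The aim (section I, Specific Aim 2).** The question is whether the navigator produces "increased levels of communication between PCPs, specialty providers and school nurses".
- **The outcome definition (section IV.A, item b).** "Providers include nurses, parents, physicians and patients".
- **The email metric (section IV.A, item b.i).** "Number of emails sent between providers will be assessed if email is used as the primary means of communication".
- **How messages are tallied (section IV.C, Study Design).** "The asthma navigator will be monitoring communications between the providers and marking the numbers of communications".
- **The planned conclusion (Summarize Knowledge to be Gained, item b).** "Utility of an asthma navigator in improving communication amongst all of a patient's medical providers".

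The survey text in section IV.C spells out its recipients as the primary care provider, the specialist and the school nurse. The introduction to section I also states a broader project goal: more communication among stakeholders, with caregivers and children named among them.

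**The concern.** The aim and the conclusion are about professionals. The definition attached to the measure also admits parents and patients. Staff who apply that definition as written would log a parent's email to a physician as communication between providers, although Aim 2 does not ask about it.

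What is at stake is how the Aim 2 count can be interpreted. If it pools two kinds of message, a rise could come from families alone while the professionals contact each other no more than before. A real gain among professionals could equally be hidden by a fall in family messages. If only a total is logged, the two parts cannot be separated afterwards, so the matter has to be settled before messages are logged.

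**Working it through.** The plan gives no figure for this outcome that could be reproduced. It states no message rate, no expected change and no sample size for Aim 2; the detectable-difference table under Power and Sample Size concerns adherence. The check is therefore a comparison of how each place uses the word *provider*, followed by one identity.

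**1. Who counts as a provider, place by place**

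| Place | Meaning |
|---|---|
| Section I, Specific Aim 2 | Primary care providers, specialists, school nurses |
| Section IV.A, item b | Nurses, physicians, parents, patients |
| Section IV.B, provider inclusion criteria | Aged 18-70 and "Caring for a patient that is enrolled in the study" |
| Section IV.C, tally by the navigator | Not defined there; the preceding sentence names the primary care provider, the pulmonary or allergy provider and the school nurse as recipients of the monthly report |
| Section IV.C, survey recipients | Primary care providers, specialists, school nurses |
| Summarize Knowledge to be Gained, item b | Medical providers |

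Only section IV.A, item b, explicitly includes families, and that is where the metric is defined. The provider criteria do not settle the matter. Patients are aged 6-17, so the 18-70 range excludes every enrolled child, but an adult parent can literally meet both criteria.

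**2. Whether another section separates the messages**

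Section IV.C describes a count of communications with no breakdown by sender or recipient. The Data Analysis Plan names tests for outcomes in general and gives no rule for the communication count. No place reconciles the two definitions.

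**3. What the pooled count can and cannot show**

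Let C be the messages among primary care provider, specialist and school nurse, and F the messages involving a parent or patient. Under the literal definition the total is T = C + F, so

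change in T = change in C + change in F.

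- If C does not change, T moves by the whole change in F.
- If F falls by as much as C rises, T does not change at all.

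Aim 2 asks about the change in C. It cannot be recovered from T unless F is recorded separately.

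**4. Which metrics are exposed**

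- Email count (item b.i): exposed, but used only if email turns out to be the main channel.
- Messaging platform (item b.ii): exposed if used. The plan describes it as possible, for a subset of teams, with the site still on a waiting list.
- Provider survey (item b.iii): not exposed. It asks for an opinion on whether the navigator helped communication, and section IV.C sends it to professionals only.

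**The case against.** The strongest reply is that the wide definition follows a stated goal. The introduction to section I wants more communication among stakeholders, families included, and no other aim measures that. On this view the definition is intended and the Aim 2 sentence is merely brief. This stands in part: the fault is a term left unreconciled, not necessarily a drafting slip, and family messages are worth counting. It does not justify pooling them into a measure whose aim and conclusion name professionals.

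A second reply is that the working text leans towards professionals. The sentence on tallying follows the list of professionals who receive the monthly report, the survey goes to professionals, and no section describes how parent-to-physician email would be captured. This also stands. Family messages *could* enter the count; the documents do not show that they *will*.

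Three stronger readings are tempting and are not supported:

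- **That Aim 2 will look positive because the programme raises family contact.** Families can see adherence data in the app, the navigator discusses barriers with them, and clinicians receive alerts. These might prompt messages, but direct access to the data could equally replace them. The direction is conjecture.
- **That the inflation can be put as a percentage.** The documents give no message rates, so any percentage would only restate assumed inputs.
- **That the provider age criterion contradicts the definition outright.** It is an enrolment criterion, not a rule for a message tally, and it excludes children but not parents.

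**Conclusion.** The point holds as a mismatch between the definition of the measure and the aim it serves. As written, the Aim 2 email count, and the platform count if there is one, may contain messages involving parents or patients. A change in either could then not be read as a change in communication among medical providers. The size and direction of any distortion are unknown.

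This rests on two conditions: that staff apply the definition in section IV.A, item b, literally, and that email or the platform is in fact used as a metric. If staff follow the narrower sense in section IV.C, the count may already be what Aim 2 needs, but the plan does not say so.

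The consequence is moderate. Adherence is the primary hypothesis, and the study is a single-group pilot that the plan itself describes as underpowered for some outcomes. Still, Aim 2 is one of three specific aims, and the correction is cheap if made before messages are logged.

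**What to change.** In section IV.A, item b:

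1. Replace the definition with one that matches Aim 2 (primary care provider, specialist, school nurse), and use it throughout the document.
2. Have the navigator record sender and recipient type for each logged message, on email and on the platform if it is used.
3. Report messages among primary care provider, specialist and school nurse as the Aim 2 count.
4. Tabulate messages involving parents or patients separately, for the broader stakeholder goal in section I. State in advance where a message addressed to both a professional and a family member belongs.

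The survey needs no change beyond keeping the recipients given in section IV.C. The cost is a revised sentence or two, one extra data field and a smaller Aim 2 count. No information is lost, because adding the two counts still gives the total.
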